#### PET-CT Flow Measures:

To calculate coronary flow reserve, measurements of regional myocardial blood flow at rest and during adenosine stress will be obtained. For this purpose, list mode data will be formatted into dynamic frames of variable length (12 frames x 5 sec, 3 frames x 20 sec, 1 frame x 300 sec). The last frame is used as a template for sectorial region of interest (ROI) analysis of the dynamic images. The input function is generated by drawing an ROI in the LV chamber on a mid-ventricular slice. This procedure yields PET absolute flow measurements in dL/min per 100 gms. The left ventricle is sampled radially from 40 different angles and 40 samples of flow are obtained for each short axis slice. The resulting hundreds of samples are grouped into 17 segments. Since the number of slices is variable, the total number of final samples will vary. Thus, for each segment we will obtain between 520 samples, from which means and standard deviations will be computed for each of the 17 regions. This procedure of repeated sampling allows a greater precision in the flow data. Coronary flow reserve is the ratio of maximum flow during stress to flow at rest. An overall measure of coronary flow reserve for the entire myocardium (across all the 17 regions) will be calculated. Secondly, regional flow reserve will be calculated according to vascular territories designated by standard techniques, i.e., left anterior descending (LAD), left circumflex (LCX), and right coronary artery (LCA). Additionally, base to apex myocardial perfusion gradients will also be quantified according to methods described by Gould and colleagues. From territorial areas, additional segmentation dividing mid and mid to apical circumferences of the left ventricle will be assigned within each polar map. Within each area, relative myocardial tracer concentrations will be quantitated by comparison to a normal database.

#### Myocardial Perfusion Defect Score:

In addition to the flow measures described above, we will construct a quantitative summed stress and rest score describing the extent and the severity of the perfusion defects across 17 segments of the myocardium. In each region, the defect severity is quantified on a 4 point scale from normal to absent perfusion. The regional severity scoring is then summed up across the 17 segments yielding a total score. Separate total scores are obtained for the rest and stress conditions, with the rest score assessing fixed or irreversible defects. A reversible defect score will be obtained by subtracting the rest score from the stress score (i.e., summed difference score). For each of the summed rest, stress, and difference scores, each patients score will be divided by the highest possible score to yield a % myocardial involvement. These scores will represent secondary outcome for statistical analysis.

#### PET for inflammation:

F18 fluorodeoxyglucose (FDG) is a glucose analog that is taken up in metabolically active cells including myocytes and tumor cells. It is also taken up in regions of inflammation. Uptake into myocytes depends on substrate, insulin

levels and GLUT4 transporter. Uptake by tumor and by regions of inflammation presumably uses GLUT1, a non insulin dependent transporter. Positron emission tomography will be performed on all patients from the base of the skull to the chest cavity after injection of F18 FDG and CT scan for neck and chest will be performed. Images will be obtained one to two to three hours after injection. Glucose levels will be checked at the time of injection using a standard clinical protocol. Uptake of tracer will be reported as global or focal and scored. Intensity of uptake will be scored according to a scale from 0 to 3. Level 0 will be no myocardial uptake. Level 1 will be myocardial uptake less than the mediastinal uptake. Level 2 will be uptake in the myocardium equal to mediastinal uptake. Level 3 will be uptake in the myocardium that is greater than mediastinal uptake. Extent of uptake will be assessed as number of specific regions of increased intensity.

A computerized program will also be utilized to assess for the standardized uptake value (SUV) which will give a continuous variable based on quantitative uptake.

CT scan images of the neck and/or chest will be fused with PET scan images to correlate the regions with regions of increased uptake.

PET-CT for the evaluation of ventricular function:

PET assessment of ventricular function is performed during gated myocardial perfusion imaging. With gated PET, accurate measurements are made of LV end-diastolic and end-systolic volumes as well as of LV ejection fraction. Additionally this method allows for assessing regional and global ventricular function both at rest and stress.

Reliability of Cardiac PET Image Reading:

The analysis of cardiac PET scans is largely automated and subject to minimal operator input. Nevertheless, we will monitor reliability of the analysis process. Inter rater and test retest reliability for analysis of cardiac PET scans will be performed prior to the start of the study with two research physicians; using 20 prior scans from previous imaging procedures. These scans will be analyzed independently while blinded to subject identity and diagnosis. For inter rater and test retest reliability, an intra-class correlation coefficient (ICC)  $>.9$  will be considered acceptable. The process will be repeated until this threshold is met. These readings will not be used in the final data analysis. All scans will be analyzed at the conclusion of the study by one of the physician raters blinded to subject identity and treatment group who will not have had contact with the study subjects or involvement in any clinical aspect of the study. Having scans read by a single rater ensures consistency of the measurement. The PET scans will be randomly sequenced for reading by subject group and treatment phase.

3 transverse CT images for the distribution of visceral fat:

Adipose tissue distribution provides an assessment of risk for the development of cardiovascular disease depending on whether is predominantly accumulated as visceral fat or not. Since patients will undergo CT imaging of the chest as part of the cardiac PET-CT imaging protocol we will take the opportunity to obtain 3 additional transverse CT images at the level of the liver, lumbar region and mid-thigh. These images will be obtained within seconds while the patient is having the PET-CT cardiac evaluation and with minimal additional exposure radiation. Fat distribution will be used in our analyses as a potential mediator or confounder of alterations in myocardial perfusion and structure.

CT imaging for Coronary Artery Calcification (CAC):

Coronary artery Calcification (CAC), a subclinical measure of atherosclerosis measured by Computer Tomography (CT) is associated with the degree of atherosclerotic plaque, and is strongly predictive of cardiovascular events including those at low risk. Coronary arterial calcification is part of the development of atherosclerosis, occurs almost exclusively in atherosclerotic arteries, and is absent in the normal vessel wall. Coronary artery calcification occurs in small amounts in the early lesions of atherosclerosis that appear in the second and third decades of life, but it is found more frequently in advanced lesions and in older age.

All subjects (RA patients and controls) will undergo cardiac CT scanning at the same time as the PET examination during study visit 1 only. Electron-beam computed tomography (EBCT) and multi-detector computed tomography

(MDCT) are the primary fast CT methods for CAC measurement at this time. Both technologies employ thin slice CT imaging, using fast scan speeds to reduce motion artifact. Thirty to 40 adjacent axial scans usually are obtained. A calcium scoring system has been devised based on the X-ray attenuation coefficient, or CT number measured in Hounsfield units, and the area of calcium deposits. For our study we will quantify CAC using the Agatston method, with a phantom of known calcium density scanned along with the participant to ensure standardization across scans. A CT study for coronary artery calcium measurement is completed within 10 to 15 min, requiring only a few seconds of scanning time.

The methodology to be used has been extensively described and standardized and can be reviewed in the reference literature below (3-5).

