## 2. STUDY DESIGN AND STATISTICAL PROCEDURES

### 2a. Study Design

(this section includes references)

For aim 1, the proposed studies will be performed in 150 patients with RA and 15 subjects without RA who will function as controls. The 150 patients will be recruited from the rheumatology clinics at New York Presbyterian Hospital of the Columbia University. The 15 control subjects will be recruited from the internal medicine clinics at the same institution or among friends of the recruited RA patients.

The 150 participants should have RA fulfilling established diagnosed criteria and not have a history of cardiovascular disease as indicated in the section for inclusion/exclusion criteria

[figure not shown]
These patients (150) will undergo the evaluations shown in the table below - and in more detail in Appendices I, II and III - during an initial visit (Visit I).

Evaluations	Visit I September/2011 - August/ 2014
Cardiac PET-CT scan*	X
3D Echocardiogram & CV Questionnaires	X RA X
Joint examination	X
Phlebotomy	X
Anthropometry	X
DEXA scan (body composition)**	X

\*including 3 transverse CT slices (mid-chest, L4-L5, mid-thigh) and cardiac CT for evaluation of coronary artery calcification (CAC).

\*\*only for the 50 participants who will be recruited for aim 2. (see below)

During the first PET scan a cardiac CT scan will be obtained in order to quantify coronary artery calcium (Agatston Score). Three additional CT Slices will be obtained (mid chest, lumbar, and mid thigh) to evaluate for visceral fat

accumulation as a risk factor for cardiovascular disease.

Controls will undergo only the PET-CT scan, 3D Echo, anthropometry evaluations, phlebotomy, and will complete abbreviated cardiovascular related questionnaires as outlined in Appendices I, II and III.

The PET-CT scan will occur on the same day or within one week of Study visit I.

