As already mentioned, the goal of this study is to investigate the "low LV mass phenotype" in patients with RA and its contributors in an attempt to elucidate the pathophysiology pathways that may connect RA with alterations in the myocardium and the evolution to heart failure. 3D-Echo will be used to measure the LV mass. Cardiac PET-CT imaging will be used to evaluate myocardial function (cardiac output, ejection fraction), microvasculature function (myocardial perfusion) and myocardial inflammation (F18-FDG uptake).

The research questions to be addressed with the study visit I are the following:

- i) Are anti-CCP antibodies or other RA-specific characteristics (e.g., disease duration, activity, severity) associated with lower LV mass (or other LV parameters of structure/function)?
- ii) What is the prevalence, the degree and correlates of microvascular dysfunction in RA? Is it associated with low LV mass or reduced global or regional contractility? Is it associated with systemic, articular and/or myocardial inflammation?
- iii) What are the prevalence, patterns, distribution and severity of inflammation as measured by F18-FDG uptake in myocardial PET imaging? Are intensity and/or distribution of F18-FDG uptake correlated with low LV mass or global or regional contractility? Does the severity/distribution of F18-FDG uptake correlate with levels of systemic and/or articular inflammation?

For the second aim of this study the goal is to evaluate the effect of TNF inhibitors on the myocardium. For the 50 patients undergoing randomization and the controls the questions to be addressed will be the following:

- i) Are global measures of LV structure (e.g., mass) or contractility (e.g., ejection fraction) affected (reduced or increased) by treatment with TNF antagonists? Is there a different effect compared to alternative therapy?
- ii) If microvascular dysfunction and/or inflammation are present before treatment, do they improve with treatment with TNF compared to alternative treatment? If parameters improve only with TNF inhibitor, this would suggest that TNF inhibitors exert a local anti-inflammatory effect on the myocardium mechanistically different compared to alternative treatment.
- iii) If treatment-induced improvements in microvascular dysfunction and/or inflammation (F18-FDG uptake) are

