## 11. POTENTIAL RISKS

A risk exists that despite all provisions to maintain participants confidentiality, confidentiality nonetheless may be compromised. As mentioned above every effort will be made to secure the data collected and separate identifying from deidentified information.

Phlebotomy is associated with minor discomfort and occasional patients may experience a more severe vaso-vagal reaction and light-headedness. A minor risk of a skin infection at the site of phlebotomy also exists but may be treated with a short course of antibiotics should it occur.

The mortality of the PET-CT imaging is low and associated mainly with the stress phase and administration of adenosine. In patients with established coronary artery disease, mortality is reported to be 2/10000 patients. The risk for an acute myocardial infarction is also reported to be 2/10000. These numbers will not be applicable to our participants as candidates with prior cardiovascular events will be screened out.

In addition the mortality at the Columbia university PET center has been 0% for PET-CT stress tests for the last 11 years with over 11000 PET-CT stress tests performed. Research participants with contraindications or risk factors for complications to PET-CT imaging and its stress phase (i.e., patients with cardiac blocks, or severe bronchospastic disease) will be excluded from the study.

The radiation exposure/dosimetry with PET-CT imaging is within FDA guidelines for research of this type. The radiation obtained during each PET examination in our protocol would be equivalent to few months of natural and cosmic radiation.

[figure not shown]
The additional 3 CT transverse images described above, the cardiac CT for CAC evaluation, and the DEXA are also associated with a small radiation exposure but no other significant risks. Female patients will be tested with a pregnancy test the morning of the day of each test associated with radiation exposure.

In addition the patients will have to be fasting overnight when they present for their study visits and this may cause mild discomfort.

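### Myocardial FDG uptake is read as inflammation without fixing uptake time, using the measured glucose or handling diabetics, which can bias aim 1 question iii and RA-control contrasts and dilute the FDG comparison in aim 2

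*Combined protocol and SAP*

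**What the plan says.** Section 2a assigns cardiac PET-CT to measure "microvasculature function (myocardial perfusion) and myocardial inflammation (F18-FDG uptake"), and aim 1 question iii asks: "What are the prevalence, patterns, distribution and severity of inflammation as measured by F18-FDG uptake in myocardial PET imaging". Section 2b likewise treats a fall in FDG intensity as a fall in myocardial inflammation.

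Section 3 (PET for inflammation) describes two routes of uptake. Of FDG in general and of normal heart muscle it says: "It is also taken up in regions of inflammation. Uptake into myocytes depends on substrate, insulin" levels and the GLUT4 transporter. For disease: "Uptake by tumor and by regions of inflammation presumably uses GLUT1, a non insulin dependent transporter". Intensity is graded 0 to 3 against the mediastinum, with an SUV as the continuous measure. Uptake is also labelled global or focal, and regions of raised intensity are counted. Glucose is checked at injection under a standard clinical protocol. On timing: "Images will be obtained one to two to three hours after injection".

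Section 6 lists diabetes as an exclusion only for the 50 randomised patients. It is not listed for the other Visit I patients or for the 15 controls.

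The only metabolic preparation stated is in section 11, as a discomfort: "the patients will have to be fasting overnight when they present for their study visits". Section 2a says: "The PET-CT scan will occur on the same day or within one week of Study visit I".

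**The concern.** By the protocol's own account, a bright myocardium can reflect what the muscle is burning and the prevailing insulin level, as well as inflammation. No rule says which grade or pattern counts as inflammation. The conditions that drive physiological uptake are only partly controlled, and the one that is measured, glucose, has no stated role in the analysis.

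Aim 1 question iii is most exposed because it rests on FDG alone. Physiological uptake graded as positive raises the prevalence. If metabolic state is related to a predictor, it can shift a correlation in either direction; if not, it weakens the correlation. RA-control contrasts are open to bias if metabolic state differs between the groups. In the mixed model of section 2a the randomised patients are free of diabetes by rule while the controls need not be. Section 2b describes the controls as otherwise similar, but the control criteria do not enforce that for diabetes.

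In aim 2, two scans of one participant may be taken under different preparation or at different intervals after injection, so the change score carries variation that is not treatment.

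**Working it through.** **1. The rules side by side**

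| Element | Stated | Not stated |
|---|---|---|
| Uptake time | 1 to 3 hours, or serial images; the sentence allows either reading | Tolerance, match across visits, or which time point gives the grade and SUV |
| Fast | Overnight, for study visits | That it covers a PET-CT done on another day within the week |
| Glucose | Checked at injection | Threshold, correction or covariate |
| Diabetes | Excluded for the 50 randomised patients | Any handling for other Visit I patients or controls |
| Pattern | Global or focal, region count | Which pattern or grade counts as inflammation |

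All of these rules can be followed while physiological uptake is counted as inflammation, or while one participant's two scans are taken at different intervals.

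**2. The plan's own figures (section 2b)**

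*Aim 1.* Detectable correlation with N = 150, 80% power, two-sided 0.05: tanh((1.960 + 0.842)/√147) = 0.227. This reproduces.

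*FDG power.* The plan claims more than 80% for a 50% decrease compared between arms. No SD, scale or within-person correlation is given, so this cannot be reproduced. Back-solving with a noncentral t, 80% power needs a standardised difference of 0.809 at 25 per arm. The SD of change can then be at most 50/0.809 = 62% of the baseline mean. With 15% drop-out (25 × 0.85 ≈ 21 per arm) the figures are 0.886 and 50/0.886 = 56%. For assumed SDs of 60, 70, 80 and 100% of the mean, power is 82, 70, 58 and 41% at 25 per arm and 75, 62, 51 and 35% at 21. Added variance from metabolic state or uptake time moves power down this scale.

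**3. Prevalence (assumed inputs)**

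Let 20% truly have inflammation and a share f of the other 80% show physiological uptake graded positive, with no true cases missed. Observed prevalence = 0.20 + 0.80f; false share of positives = 0.80f/(0.20 + 0.80f).

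| f | Observed prevalence | False share of positives |
|---|---|---|
| 0.10 | 0.28 | 0.08/0.28 = 29% |
| 0.20 | 0.36 | 0.16/0.36 = 44% |
| 0.30 | 0.44 | 0.24/0.44 = 55% |

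**4. Aim 1 correlations (assumed reliability)**

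Let λ be the reliability of FDG as a measure of inflammation, with error unrelated to the predictor. The true correlation needed for 80% power is 0.227/√λ. Power at a true 0.227 is Φ(atanh(0.227√λ)·√147 − 1.960).

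| λ | True correlation needed | Power at 0.227 |
|---|---|---|
| 0.8 | 0.254 | 70% |
| 0.6 | 0.293 | 58% |
| 0.4 | 0.359 | 42% |

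**5. Dilution in aim 2 (assumed share)**

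Start from exactly 80% power for a 50% fall in total signal and hold the SD fixed. If only a share s of the signal is inflammatory and only that part halves, the total falls by 50s%. Noncentral-t power is 56% at s = 0.75, 29% at s = 0.50 and 10% at s = 0.25. The results are the same at 25 and 21 per arm, because each starts from its own 80% SD.

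**The case against.** **A reader might infer that the randomised comparison is biased.** The documents do not support that. Diabetics are excluded there, allocation is random, and section 3 (Reliability of Cardiac PET Image Reading) has one rater, blinded to treatment, read the scans in random sequence. Nothing ties preparation or uptake time to arm. Within-arm change, read without a comparator, is less protected. The 15 controls are rescanned at six months to show normal variation, which helps gauge it but does not remove it.

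**A reader might also infer that aim 2 questions ii-iv stand or fall with FDG.** They do not: each is also put in terms of microvascular function or perfusion, which is measured with ammonia PET.

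**Nor is it right that the plan has no control.** The overnight fast and the global/focal recording are partial controls. PET-CT is itself listed as a visit evaluation, the one-week allowance is given for Visit I only, and that an off-day scan would be unfasted is inference. The standard clinical protocol for glucose, or the exclusion for contraindications to FDG, could hold a site rule not seen here. The timing sentence may mean serial imaging.

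**Confounder adjustment is planned.** Section 2a adjusts associations with LV measures and allows further covariates in the mixed models. It does not name glucose or diabetes, although section 6 does name statins as a possible interference with the FDG reading. Adjusting associations does not correct a prevalence.

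**No count of affected diabetic scans can be given.** The documents state neither the share of diabetics nor the direction or frequency of the effect. The reader-agreement check on 20 earlier scans does not answer the point either: it tests the reading, not the participant's metabolic state or the uptake time.

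**Conclusion.** The point holds. The protocol describes a physiological source of myocardial FDG uptake and then reads uptake as inflammation, with the uptake time unfixed, glucose without a stated use, and diabetics admitted at Visit I and among the controls. The main consequence is possible bias in aim 1 question iii and in RA-control contrasts. In the randomised comparison it is mainly noise and dilution, confined to the FDG part of questions ii-iv.

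The size cannot be derived from the documents. The 28-44% observed prevalence rests on an assumed 20% true prevalence and assumed 10-30% physiological positives among the rest. The power and correlation figures rest on assumed signal shares and reliabilities. They show sensitivity and are not estimates. Label: cheap improvement.

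**What to change.** 1. In section 3 (PET for inflammation), name one uptake time with a narrow tolerance, or, if serial images are meant, the time point that supplies the grade and SUV. Record the actual time and keep it the same for each participant at Visits I and II.
2. Reconcile the fast in section 11 with the one-week PET-CT allowance in section 2a, so that the stated preparation applies to the scan day and is the same at both visits.
3. Include Visit I glucose at injection as a covariate in the aim 1 FDG models. In aim 2 use only the baseline value. Follow-up glucose is measured after randomisation and could itself reflect treatment, so it belongs in a sensitivity analysis.
4. Repeat the aim 1 FDG prevalence and correlation analyses without diabetics. Report diffuse and focal uptake separately, without presuming that only focal uptake is inflammation; the documents do not say so, and that reading could discard diffuse inflammation.

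Glucose and pattern are already collected, so no new test is needed. The cost is tighter scan scheduling and a little extra analysis. Items 1 and 2 must be settled before scanning, because uptake time and preparation cannot be standardised afterwards.
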